5.4 Early Withdrawal

Removal of Study Participants:

The removal of a study participant will be based on the Clinical, and Protocol Violation conditions outlined below. If possible, any evaluations or assessments planned for the end of the study will be completed at an Early Termination (ET) Visit. Criteria for participant removal at the PI's discretion are:

Removal by Principal Investigator

The removal of a study participant by the principal investigator will be based on the Clinical and Protocol Violation conditions outlined below. If possible, any evaluations or assessments planned for the end of the study will be completed at an Early Termination (ET) Visit. Criteria for participant removal at the PI's discretion are:

Clinical

A participant may be withdrawn from the study if, in the opinion of the PI, it is not in the best interest of the participant to continue. Participants who experience an adverse event (AE) or

severe adverse event (SAE) will be assessed by the PI and determine if removal from the study is necessary. Participants experiencing a SAE will be followed up by PI until resolution of SAE. Any female who becomes pregnant during the course of the study will be removed and followed-up with accordingly.

Protocol Violation

Protocol violations may be a result of the above inclusion/exclusion criteria. Violations will be assessed by the PI on a case-by-case basis with removal from the study, if necessary. Participants can be withdrawn from the study at the discretion of the Sponsor. Participants who are deemed to be a protocol violation will not be followed up on.

6. Investigational Product

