10.1. Adverse Events

Definition:

An unexpected event (i.e., medical occurrence, sign, or symptom) that happens during the study period with an investigational product. Adverse event (AE) may be mild, moderate, or severe, and may be caused by something other than the drug or therapy being given. Adverse events must be followed-up to resolution or when the condition is deemed stable by the PI.

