10.2. Collecting, Recording, and Reporting of AEs

Collection:

The PI of delegated study staff must record all adverse events in an AE form with information about:

- Details of adverse event
- Date of onset (time can be recorded, if applicable)
- Intensity (mild, moderate, severe)
- Causal relationship to trial involvement (probable, possible, unlikely, not related)
- Other actions taken
- Date and time of outcome
- Outcome

Reporting:

The following timelines apply to the reporting of AEs/SAEs as applicable:

- Within 24 hours of the PI becoming aware of the event if it results in death of a participant

- Within 2 weeks (10 business days) after becoming aware of the event if:
 - It is an AE which is related to the conduct of the study;
 - It is an AE that is expected (listed in the ICF as a potential side effect) but is occurring more frequently than expected;
 - It is an unexpected AE/SAE that is related to the conduct of the study but is not life-threatening
- Annually (together with the Study Status Report) if:
 - It is an expected AE (listed in the ICF as a potential side effect);
 - It is an unexpected AE that is unlikely to be related to the conduct of the study and is not life-threatening.

Severity Assessment

All clinical events will be graded as mild, moderate, or severe according to the following scale:

Mild - The adverse event does not interfere in a significant manner with the subject's normal functioning level.

Moderate -The adverse event produces some impairment of functioning but is not hazardous to the subject's health.

Severe -The adverse event produces significant impairment of functioning and may be potentially hazardous to the subject's health.

Causality Assessment:

Certain – An adverse event that cannot be explained by disease or any other drugs.

Probably/Likely – An adverse event that follows a known, expected or suspected response pattern of the drug and is unlikely to be explained by any other factors or another etiology.

Possible – An adverse event that follows a known, expected or suspected response pattern of the drug but could readily have been produced by a number of other factors or explained by another etiology.

Unlikely – An adverse event that does not follow a known, expected, or suspected response pattern of the drug and could readily have been produced by a number of other factors or explained by another etiology.

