10.5. Treatment and Follow-Up of Laboratory Abnormalities

All events will be treated in accordance with GCP to resolution or until stabilized as deemed by the PI and/or delegate

11. Statistical Evaluation

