11.2. Study Population

Intention-to-treat (ITT) analysis will be considered in this study. ITT analysis includes every subject who is randomized according to randomized treatment assignment. The ITT analysis includes all randomized patients in the groups to which they were randomly assigned, regardless of their adherence with the entry criteria, regardless of the treatment they actually received, and regardless of subsequent withdrawal from treatment or deviation from the protocol. ITT analysis reflects the practical clinical scenario because it admits noncompliance and protocol deviations. ITT analysis maintains prognostic balance generated from the original random treatment allocation and it gives an unbiased estimate of treatment effect.

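### Section 5.4 ends follow-up of protocol violators with no safety exception, which conflicts with section 10.1 when a removed violator has an adverse event that is still open

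*Combined protocol and SAP*

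**What the plan says.** Section 5.4 (Early Withdrawal) sets out two grounds for removal, Clinical and Protocol Violation. For both it plans a closing visit: "If possible, any evaluations or assessments planned for the end of the study will be completed at an Early Termination (ET) Visit".

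The Clinical paragraph has the PI assess participants with an AE. For serious events it adds "Participants experiencing a SAE will be followed up by PI until resolution of SAE". It also requires follow-up of any participant who becomes pregnant. It does not say how long a non-serious AE is followed.

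The Protocol Violation paragraph leaves removal to judgement: "Violations will be assessed by the PI on a case-by-case basis with removal from the study, if necessary". It ends with "Participants who are deemed to be a protocol violation will not be followed up on".

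Section 10.1 gives the general duty: "Adverse events must be followed-up to resolution or when the condition is deemed stable by the PI". Section 10.5, headed as dealing with laboratory abnormalities, says "All events will be treated in accordance with GCP to resolution or until stabilized as deemed by the PI and/or delegate". Neither section mentions violators or removed participants.

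**The concern.** A site that removes a violator while an AE is still running finds two instructions. Section 5.4 tells it to stop following the participant, and 10.1 tells it to continue until the event resolves or is judged stable. It cannot do both, and the protocol gives no order of precedence.

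The stake is participant safety first and completeness of the safety record second. Safety is the first secondary objective. The AE form in section 10.2 asks for the outcome and for "Date and time of outcome". If contact ends under 5.4, both can stay blank for an event that 10.1 meant to be tracked to its end.

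Violators can be people with an open safety question. Section 12 allows a deviation that raises a participant's risk of harm to be classed as a violation. Section 5.4 says violations may arise from the eligibility criteria, and these include safety exclusions such as sensitivity to an ingredient or a history of anaphylaxis.

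**Working it through.** No figure in the plan is at issue and no arithmetic applies. The check sets the rules side by side and goes through the cases for a violator who has been removed.

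**Rules compared**

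- 5.4, last sentence of Protocol Violation: no follow-up, no exception.
- 5.4, Clinical: SAEs followed until resolution and pregnancies followed up; no statement that this overrides the violator sentence.
- 5.4, ET visit: applies to both grounds for removal, but only where possible.
- 10.1: AEs must be followed to resolution or until the PI judges the condition stable; no exemption.
- 10.5: events treated to resolution or stabilization; no exemption. This is secondary support, because it speaks of treatment and sits under a laboratory heading.

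**Cases**

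1. The participant has no AE, or only AEs that have resolved. No conflict, whether or not an ET visit takes place.
2. A non-serious AE is unresolved but judged stable by the PI at removal or at the ET visit. No conflict, because the 10.1 endpoint has been reached.
3. A non-serious AE is neither resolved nor judged stable after the ET visit. Conflict: 10.1 requires follow-up to continue and 5.4 ends it.
4. A non-serious AE is neither resolved nor judged stable at removal, and no ET visit takes place. The same conflict.
5. An SAE is unresolved. The Clinical paragraph requires follow-up to resolution and the violator sentence says there is none, so 5.4 disagrees with itself. The Clinical rule gives a site good reason to continue, which makes the gap less sharp than in cases 3 and 4.
6. A pregnancy. As for case 5: the Clinical paragraph requires follow-up, but the violator sentence does not carve it out.

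The contradiction with 10.1 is therefore plainest in cases 3 and 4. A missing ET visit creates no conflict unless an AE is open.

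**Could the sentence refer only to study visits?** The Clinical paragraph just above it uses the same expression for safety follow-up of SAEs and pregnancies, and 10.1 uses it for AEs. A reader who has met it in that sense can reasonably take the violator sentence to cover safety follow-up too. The visits-only reading is possible, but the text does not secure it.

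**The case against.** The best reply is that this is ambiguity more than contradiction. Section 5.4 gives removed violators an ET visit, so the sentence cannot mean no contact at all; read in context, it may mean only that study visits end. There are also several backstops. The PI assesses anyone with an AE. Visit 5, whose assessments the ET visit repeats where possible, includes an AE review and safety bloods, and section 8 has participants contacted about laboratory results of concern. The PI who decides on removal can judge stability at the same time.

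Most of this stands, and it is why the point is narrow. It does not close the gap: the ET visit is conditional, a single visit does not follow an event that is still unstable afterwards, and the limit to study visits is not written down.

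A reader might go further in three ways that the documents do not support.

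- One might infer that every violator without an ET visit is a breach of 10.1. Case 1 shows that this is not so.
- One might treat 10.5 as an equal second contradiction. Its heading and its wording about treatment make it weaker than 10.1.
- One might infer that the sentence undermines the primary analysis, because section 11.2 keeps participants in the ITT analysis "regardless of subsequent withdrawal from treatment or deviation from the protocol" while a violator removed early could lack Day 7 TNSS and PNIF values. Any such loss would come from removal itself. The ET visit would collect both measures where possible, and nothing in the documents shows that this sentence changes the primary data.

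**Conclusion.** The point holds in its narrow form. The last sentence of 5.4 is wrong as written: for a removed violator with an AE that is neither resolved nor judged stable at removal or at the ET visit, following it breaks 10.1. Severity is minor.

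The size cannot be estimated. The documents give no rate for violations, removals, AEs, or AEs still open at removal, and the number affected is probably small. No effect on the primary analysis, sample size, power or type I error is claimed.

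The conclusion assumes that the sentence concerns removed violators, since those kept in the study continue their visits, and that follow-up carries the same meaning here as elsewhere in 5.4 and in 10.1. If the sponsor intended only that study visits stop, the fault is one of wording, and the remedy is the same.

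**What to change.** Replace the last sentence of the Protocol Violation paragraph in 5.4 with wording such as:

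*Participants removed for a protocol violation will have no further scheduled study visits after the ET visit, except that ongoing AEs will be followed to resolution or until deemed stable by the PI (section 10.1), SAEs will be followed until resolution, and pregnancies will be followed up, as required in this section.*

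The wording makes explicit that the rule applies to removed participants. SAEs are named separately because the Clinical paragraph of 5.4 requires resolution, so one endpoint of resolution or stability for all events would weaken that standard and create a new inconsistency. Pregnancy is named because 5.4 already requires its follow-up.

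The cost is one sentence in an amendment and a few safety contacts that 10.1 and the Clinical paragraph already call for. The analysis plan needs no change.

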6.1 Investigational Product Details

Unit dose: 1 lozenge (8g)

Package size: 1 box containing 8 lozenges

Ingredients: sucrose (cane sugar), L-arginine, honey, trehalose, lactose, inulin, D-mannose, corn syrup, coconut oil, calcium gluconate, calcium lactate, carrageenan, cocoa powder, sodium chloride (salt), cinnamon, vanilla extract.

6.2 Manufacturing and Storage

AllerPops is manufactured at:

QINGDAO XIZHITANG FOOD CO., LTD.

[name]

Chengyang District

Qingdao, Shandong, China

The product will be shipped by the Sponsor to the CRO prior to trial commencement. The CRO will be responsible for storing, maintaining, and dispensing the product accordingly. The product will be stored at room temperature in a limited-access location. Temperature of the storage location will be checked and recorded as per the site's SOPs.

6.3 Labelling

The IP will be labelled according to Health Canada and ICH-GCP E6(R2) guidelines and will contain the following information in both official languages (English and French):

- a statement indicating that it is an investigational product to be used only by a qualified investigator
- the brand name or code of the study product(s)
- the expiry date
- the storage conditions
- the lot number

- the name and address of the manufacturer and the sponsor
- the protocol code or identification

Written instructions on how to use the investigational product will be provided to the participant as part of the Informed Consent Form.

6.4 Directions

IMPORTANT: Must be fasting for at least 4 hours before taking the study product.

Directions for the Investigational Group:

1. Brush teeth with tap water (no toothpaste).
2. Scrub tongue with disposable tongue scraper provided. (**Caution:** *reaching too far may cause a gag reflex.*)
3. Gargle and swish hot (optimal 120°F) water for 10-20 seconds. Spit out and repeat gargling over the next 5 minutes. The tongue should be red and without any biofilm. If it is not, repeat *Step 2*, and gargle once more.
4. Self-administer one lozenge. Let the lozenge slowly melt in the mouth. Do not chew or swallow whole. This may take up to 60 minutes. Discard if it is not fully dissolved after 60 minutes. Wait at least 30 minutes before eating your next meal.
5. Repeat *Step 1* to *Step 5* every other day for a minimum of 3 doses.
6. After the 3rd dose, you may repeat *Step 1* to *Step 5* every other day until you are satisfied with the symptom relief up to and including Day 13. Do not take the product on Day 14 onwards and return all remaining product at Visit 4.

Directions for the Control Group:

1. A box containing 8 units of the Investigational Product will be dispensed. This box will only be dispensed once, at visit 2.
2. Microwave: heat the product in 5 second increments until soft. (Caution: more than 10 seconds of microwaving the product may cause it to burn).
3. Cut: cut the product into smaller pieces those are the size of your usual medication/supplement.
4. Swallow: Participant will be instructed to swallow each of the small pieces over time with plenty of warm water. The participant will also be allowed to have a few sips of water to moisten the mouth and throat prior to swallowing the control product, if they feel it is necessary. Wait at least 30 minutes before eating your next meal. For next 2 doses, you must repeat *Step 2* to *Step 4* once every other day (day 3 and day 5).
5. After the 3rd dose, you may choose to use additional doses until you are satisfied with the symptom relief. If you choose to continue using the product, you must repeat *Step 2* to *Step 6* once every other day up to (and including) day 13. Maximum dose expected during day 1 to 13 is 7. Do not take the product on day 14 onwards and return all remaining product at visit 4.

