For the control group, the same investigational product will be administered, however the procedure for use will be modified as follows: There will be no mouth cleaning before the product consumption (No step 1 as mentioned above). The product will be swallowed instead of dissolved in the mouth, in order to reduce its presence in the mouth as much as possible. The purpose of this control group is to support the effect of use of the entire two-step method as compared to the investigational group.

The active ingredient, L-Arginine is known to Health Canada. L-Arginine is listed in the NHPID, and allowed for use in NHPs under proposed here conditions of use. Safety of the of current ingredient combination, while allowed for use separately, will also be tested under proposed conditions of use.

The Rationale for Performing Research:

Increase in immune-mediated conditions [30]–[32](Allergic rhinitis is one of them) and the few medical solutions available (each of which is associated with side effects) prompted this research and clinical study. The medicinal ingredient, L-Arginine, in the formulation of AllerPops is a well-known Natural Health Product Ingredient with history of human use.

4. Study Objectives

Objectives:

Primary Objective: To assess the effectiveness of AllerPops on relieving nasal symptoms compared to the control group in volunteers with seasonal and perennial (or intermittent and persistent) allergic rhinitis during the first 7 days of the 21-day intervention period.

Secondary Objectives:

1. To evaluate the safety of AllerPops administration in volunteers with seasonal/year-long allergies during a 21-day intervention period.
2. To assess the duration of effectiveness of AllerPops in relieving nasal symptoms compared to the control group in volunteers with seasonal/year-long allergies during a 21-day intervention period (exploratory).

3. To evaluate the effect of the AllerPops administration on the oral microbial presentation/microbiota using Amplicon Metagenomics Sequencing test through saliva samples during a 21-day intervention period (exploratory).
4. To evaluate the effect of the AllerPops administration on the IgE (total) blood level during a 21-day intervention period (exploratory).

Endpoints:

Primary Endpoint: The reduction of nasal allergic symptoms during the first 7 days of the 21-day intervention period (once every other day – D1, D3, D5). The reduction of symptoms will be measured using the following assessments.

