After completion of treatment dose, the participants are allowed for extra 4 maintenance doses, at a maximum frequency of once every other day (on day 7, 9, 11, and 13). Participant will not take the product on day 14 and onwards, and must return all remaining product at visit 4. Between day 7 and day 13, the participants may take AllerPops with any recurrence of nasal allergy symptoms or until the participant is satisfied with the relief of the nasal allergy symptoms, as long as the minimal interval of alternate day dosing is not violated. The participant will continue to fill out a daily diary to indicate the time of dosing, symptoms, AEs (such as fatigue, fever or headache), and concomitant medications, if applicable.

Visit 4 – Follow-Up – Day 14 ± 2

These assessments may not be completed in the order shown below.

Participants:

1. Do not need to fast prior to this visit.
2. Will have any changes to health reviewed by delegated study staff.
3. Study diary will be collected and/or reviewed by delegated study staff for completion, and any AEs and/or concomitant medications.
4. Will have the following measurements taken: temperature, blood pressure, heart rate.
5. Will complete the following assessments:
 - Total nasal symptoms score (TNSS) questionnaire
 - Peak nasal inspiratory flow (PNIF) measurement
6. Be reminded to complete daily diary.

The participant will continue to fill out a daily diary to indicate symptoms, AEs (such as fatigue, fever or headache), and concomitant medications, if applicable.

After this visit, the participant will not continue taking the IP. Any remaining IP will be collected from the participant at this visit.

Visit 5 – End of Study – Day 21 ± 2

These assessments may not be completed in the order shown below.

Participants:

1. Must be at least 8 hours fasting (no food, only water) prior to visit.
2. Will have any changes to health reviewed by delegated study staff.
3. Study diary will be collected and reviewed by delegated study staff for completion, and any AEs and/or concomitant medications.
4. For females of childbearing potential, a urine sample will be collected for a urine pregnancy test.
5. Will have the following measurements taken: temperature, blood pressure, heart rate.
6. Will have the following saliva test:
 - Amplicon Metagenomics Sequencing
7. Will complete the following assessments:
 - Total nasal symptoms score (TNSS) questionnaire
 - Peak nasal inspiratory flow (PNIF) measurement

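### Section 6.4 words the optional-dose rule for Days 7 to 13 differently by arm, and the control wording can be read two ways (minor)

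*Combined protocol and SAP*

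**What the plan says.** Four places in the combined protocol and SAP govern dosing after the three required doses.

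- **Section 6.4, Investigational Group, step 6:** once the required doses are done, "you may repeat *Step 1* to *Step 5* every other day until you are satisfied with the symptom relief up to and including Day 13".
- **Section 6.4, Control Group, step 5:** first, "you may choose to use additional doses until you are satisfied with the symptom relief". Then: "If you choose to continue using the product, you must repeat *Step 2* to *Step 6* once every other day up to (and including) day" (Day 13). The step goes on: "Maximum dose expected during day 1 to 13 is 7".
- **Section 8, Visit 3 (both arms):** "the participants are allowed for extra 4 maintenance doses, at a maximum frequency of once every other day (on day 7, 9, 11, and 13"). In that window, "the participants may take AllerPops with any recurrence of nasal allergy symptoms or until the participant is satisfied with the relief", provided the alternate-day spacing is kept.
- **Synopsis, Duration (both arms):** at least three doses, then continuing until the participant is satisfied.

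Section 3 describes the control thus: "the same investigational product will be administered, however the procedure for use will be modified as follows". It then names two changes: no mouth cleaning, and swallowing instead of dissolving. A different rule for ending optional doses is not named. Section 6.5 says that participants take home an envelope with a dosing instruction sheet. Section 9.8 limits the compliance calculation to Visit 3. The daily diary records dosing times after Visit 3.

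**The concern.** Only the control directions attach a *must* to optional dosing. A control participant who takes that sentence at face value and continues at Day 7 would take every optional dose through Day 13. An investigational participant who continues may stop after one. The arms would then differ in number of doses and in days off product because of how their directions are worded. Such a difference follows allocation, so the intention-to-treat analysis in Section 11.2 cannot remove it. No planned summary would reveal it either, because compliance is not calculated after Visit 3.

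The results at stake are the exploratory Day 14 TNSS and PNIF comparisons and the exposure behind the 21-day safety comparison. Duration of effect and safety are both listed secondary objectives, so exposure after Day 7 matters for reading them.

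**Working it through.** **1. The plan's own dose count.** Alternate-day doses fall on Days 1, 3, 5, 7, 9, 11 and 13. That is 3 required + 4 optional = 7, which agrees with the maximum in control step 5 and the four maintenance doses at Visit 3.

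**2. What each reading permits.** Days off product = visit day − day of last dose, for consecutive dosing and visits on the nominal day.

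| Last dose (day) | Total doses | Days off at Day 14 | Days off at Day 21 |
|---|---|---|---|
| 5 | 3 | 9 | 16 |
| 7 | 4 | 7 | 14 |
| 9 | 5 | 5 | 12 |
| 11 | 6 | 3 | 10 |
| 13 | 7 | 1 | 8 |

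Investigational step 6 allows every row. Control step 5 read as a spacing rule also allows every row. Control step 5 read as a commitment allows only the first and last rows.

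**3. Illustrative size at Day 14.** The documents give no continuation rates and no rate at which an effect fades, so these inputs are assumptions:

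- c: probability of taking a further optional dose after each one, for participants who stop when satisfied: 0.5, 0.7 or 0.9.
- p: share of each arm that continues at Day 7: 1 or 0.5.
- s: share of continuing control participants who follow the commitment reading: 1 or 0.25. The others behave like the investigational arm.
- Equal true effect in both arms: 0.6 SD at the last dose (the effect size in Section 11.1), falling linearly to zero over 7 days off product.

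Mean optional doses when stopping on satisfaction = 1 + c + c² + c³ = 1.88, 2.53, 3.44, against 4 under the commitment reading.

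Mean days off at Day 14: D = 7 − 2(c + c² + c³) = 5.25, 3.93, 2.12, against 1.

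False difference favouring control = p × s × 0.6 × (D − 1)/7. For c = 0.5 and p = s = 1: 0.6 × 4.25/7 = 0.364 SD.

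| p | s | c = 0.5 | c = 0.7 | c = 0.9 |
|---|---|---|---|---|
| 1 | 1 | 0.364 | 0.251 | 0.096 |
| 0.5 | 1 | 0.182 | 0.126 | 0.048 |
| 1 | 0.25 | 0.091 | 0.063 | 0.024 |
| 0.5 | 0.25 | 0.046 | 0.031 | 0.012 |

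For scale only: a two-sided 0.05 t test with 36 per arm would reject 33% of the time at 0.364 SD and 5.5% at 0.048 SD.

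**4. Day 21.** The last permitted dose is on Day 13, so a Day 21 visit is at least 8 days off product. Under the 7-day fade the false difference is 0. At the earliest visit in the window (Day 19, 6 days off) it is at most 0.6 × 1/7 = 0.09 SD.

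**5. Primary comparison.** It rests on the doses of Days 1, 3 and 5. A visit on Day 6 precedes any optional dose, and participants are told not to dose on the morning of Visit 3. Only a Visit 3 on Day 8, at the end of its ±1 window, could follow a Day 7 optional dose.

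**The case against.** The strongest reply is that the commitment reading is the weaker reading of the text. The sentence just before it makes control dosing depend on satisfaction. Control step 4 uses the same *must repeat* phrasing for procedure and spacing, and the Day 13 limit matches the investigational one. The synopsis and the Visit 3 text make dosing satisfaction-based for everyone. This stands: the control text is ambiguous, not plainly all-or-nothing. It does not remove the problem, because an ambiguity in one arm's directions is still a difference between arms.

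Three further limits also stand. The instruction sheets are not among the documents, so that they repeat Section 6.4 is an inference. Participants can also put questions to unblinded staff and receive dosing reminders. Section 3 does not say that its two changes are the only differences between the arms. And dose counts could differ under identical wording if relief differs, since stopping depends on satisfaction; common wording removes only the part due to instruction.

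A reader might infer that all later endpoints are biased at Days 14 and 21, or that the false-positive rate reaches 33%. The documents support neither. IgE and saliva are not sampled at Day 14, and at Day 21 the assumed fade leaves no difference. The 33% needs every participant to continue and every control participant to follow the disputed reading. It also needs a Day 14 t test, whereas Section 11.3.3 plans exploratory data analysis for secondary variables other than safety. No calculation here quantifies an effect on adverse events.

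**Conclusion.** The inconsistency is real and minor. Section 6.4 words the optional-dose rule differently by arm, the control wording supports two readings, one of them contradicts other parts of the protocol, and the recurrence provision at Visit 3 is in neither arm's directions. Whether this would produce an imbalance depends on how many control participants follow the commitment reading, which the documents cannot show.

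Under the stated assumptions the false Day 14 difference lies between about 0.01 SD (half continue, a quarter of continuing control participants take the commitment reading, c = 0.9) and 0.36 SD (all continue, all take it, c = 0.5). It would favour control, that is, work against the investigational method. The exposure imbalance also bears on the safety comparison, with no size given. The primary result is not in question at a Day 6 or Day 7 visit.

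**What to change.** Reconcile the synopsis, both sets of directions in Section 6.4 and the Visit 3 maintenance paragraph. One identically worded optional-dose rule, covering when a dose may be taken, when to stop and whether dosing may restart, should appear in both arms' directions and in the instruction sheets based on them. Which rule applies is for the sponsor and investigator to decide.

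Correct the step references: control step 5 cites a step that its list lacks, and investigational step 5 tells participants to repeat a range that includes itself.

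Tabulate the number of optional doses and the day of last dose by arm, from the diary, beside the Day 14 and Day 21 results.

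The cost is an amendment with its ethics and regulatory review, reworded instruction sheets, and one descriptive table from data already collected. It needs no extra visits, procedures or participants.
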